#### 4. SUBJECT SELECTION

A total of 36 subjects with histologically-confirmed basal cell skin cancer who meet all eligibility criteria will be enrolled. Patients with mBCC will be excluded.

##### 4.1 INCLUSION CRITERIA

Subjects must meet all of the following inclusion criteria to be eligible for enrollment into the study:

1. Evidence of a personally signed and data informed consent document indicating that the subject (or legally acceptable representative) has been informed of all pertinent aspects of the trial.
2. Subjects who are willing to comply with scheduled visits, treatment plan, laboratory tests, and other study procedures.
3. Be 18 years of age or older at the time of informed consent.
4. Has one or more clinically suspicious lesions for BCC at Pre-Study screening Visit that is/has:
  - a. a diameter  $\geq$  6 mm if located on the “mask areas” of face (central face, eyelids, eyebrows, periorbital, nose lips [cutaneous and vermillion], chin, mandible, preauricular and postauricular skin/sulci, temple, ear), genitalia, hands, or feet (See Appendix 2 for Figure of “mask areas” of face)
  - b. a diameter  $\geq$  10 mm if located on cheeks, forehead, scalp, or neck
  - c. a diameter  $\geq$  20 mm if located on trunk and extremities

or has a lesion suspicious for locally advanced BCC defined as a lesion that:

- a. is  $\geq$  10 mm,
  - b. has recurred following surgery or surgical resection would result in substantial deformity, and
  - c. has been deemed not appropriate for radiation.
5. Have a histologically-confirmed BCC prior to first dose of study drug at Treatment Initiation Visit (Baseline/Day 1).
  6. Have an Eastern Cooperative Oncology Group (ECOG) performance status of 2 or less at Baseline/Day 1 visit. (See Appendix 3, ECOG Performance Status)
  7. Males and females must agree that they have no desire or plan to conceive children in the future
  8. Female of reproductive potential must use 2 effective methods to avoid pregnancy during therapy and for 9 months after completing therapy. Effective methods must be used for 1 month before initiating therapy.
  9. Male patients must use effective measures to avoid pregnancy in their partner at all times, even after vasectomy, during treatment and for 3 months after the last dose.
  10. Agreement not to donate blood or blood products during the study and for 9 months after the last dose.
  11. Subjects with Basal Cell Nevus Syndrome are eligible for enrollment.

**EXCLUSION CRITERIA**

Subjects presenting with any of the following will not be included in the study:

1. Women who are pregnant or lactating, or planning pregnancy while enrolled in the study.
2. History of prior treatment with vismodegib or any Hh Pathway Inhibitor
3. Have evidence of clinically significant and unstable diseases or conditions such as cardiovascular, immunosuppressive, hematologic, hepatic, neurologic, renal, endocrine, collagen-vascular, or gastrointestinal abnormalities. Subjects with clinically stable chronic medical conditions including, but not limited to, controlled hypertension, diabetes mellitus type II, hypercholesterolemia, or osteoarthritis, will be allowed to enter the study.
4. Have any dermatological disease at treatment site that the investigator thinks may be exacerbated by treatment with vismodegib or cause difficulty with examination (e.g., psoriasis, eczema).
5. The target lesion identified at Pre-study Screening visit has been determined to be mBCC by radiological assessment prior to first dose of study drug.
6. Inability or unwillingness to swallow capsules.
7. Have a history of infection requiring hospitalization, parenteral antimicrobial therapy, or as otherwise judged to be clinically significant by the investigator within 4 weeks prior to first dose of study drug.
8. Have a history of infection requiring antimicrobial therapy within 2 weeks prior to first dose of study drug.
9. Have a history of alcohol or substance abuse, unless in full remission for greater than 6 months prior to first dose of study drug
10. Known to be infected with human immunodeficiency virus (HIV), hepatitis B or hepatitis C viruses.
11. Participation in other study using an investigational or experimental therapy or procedure within 4 weeks or 5 half-lives (whichever is longer) before the study begins and/or during study participation. Subjects cannot participate in studies of other investigational or experimental therapies or procedures at any time during their participation in this study.
12. Other severe acute or chronic medical or psychiatric condition or laboratory abnormality that may increase the risk associated with study participation or investigational product administration or may interfere with the interpretation of study results and, in the judgment of the investigator, would make the subject inappropriate for entry into this study.
13. Subjects who are investigational site staff members or subjects who are Sponsor employees directly involved in the conduct of the trial.
14. A subject who, in the opinion of the investigator or sponsor, will be uncooperative or unable to comply with study procedures.
15. Subjects (male and female) who desire to conceive in the future

## 5. **INFORMED CONSENT**

Prior to entering the study, the investigator or designated assistant will explain to each subject or legally acceptable representative, the nature of the study, its purpose, procedures, expected duration, and the benefits and risks involved in study participation.

Alternative therapies for treatment of BCC (e.g. surgical excision, Mohs surgery, radiation therapy, imiquimod topical treatment, 5-fluorouracil topical therapy, electrodesiccation and curettage, cryotherapy and photodynamic therapy) will be discussed with the subject. Subjects will be informed that declining to participate or withdrawal after enrollment in trial will in no way affect the management or care of the patient.

Each subject will be given an information and consent document and the opportunity to ask questions; and will be informed of his/her right to withdraw from the study at any time without prejudice. After this explanation and before any study-specific procedures have been performed, the subject, or legally acceptable representative, will voluntarily sign and date an informed consent statement. Prior to participation in the study, the subject or his/her legally acceptable representative should receive a copy of the written informed consent form and any other written information provided to the subject. (See Appendix 4 for information on required elements of informed consent.)

## 6. **STUDY METHODOLOGY**

### 6.1 **STUDY PROCEDURES**

The following sections describe in detail all study procedures. A flow chart of study procedures is presented at the end of the protocol (Appendix 6).

#### 6.1.1 Pre-study Screening visit

Subjects will be screened within 4 Weeks (+/-3 days) prior to the Treatment Initiation (Baseline/Day 1) visit to confirm that they meet the entrance criteria for the study. The study investigator or sub-investigator will discuss with each subject the nature of the study, its requirements, and its restrictions. Written informed consent must be obtained prior to performance of any protocol-specific procedures.

The following procedures will be performed at Pre-study Screening visit, within 4 weeks prior to Treatment Initiation (Baseline/Day 1, Visit 2) visit

- Confirmation of inclusion criteria, excluding histologic confirmation of basal cell skin cancer of target lesion.
- Identification of skin lesion(s) clinically suspicious for basal cell skin cancer.
- Recording of medical history. (Medical history is defined as a disease or syndrome that is ongoing at or stopped before Informed Consent.)

- Recording of history of alcohol and drug use, smoking status (current smoker, current heavy smoker >20 cigarettes per day), and average weekly alcohol consumption (units/week), where a unit contains 12 g of pure alcohol, an amount equivalent to that contained in 5 oz (a glass or 148 mL) of wine, 12 oz (355 mL) of beer, or 1.5 oz (44 mL) of 90 proof of spirits. (The intent is to monitor the subject's alcohol consumption during the study to determine if it has impact on the efficacy, disease state and any co-morbidities. It is the PI's discretion to determine acceptable levels of consumption or abuse. Alcohol and/or substance abuse are exclusionary.)
- Recording of current medications and all other drugs (including non-prescription drugs, vitamins, and dietary supplements) taken within 4 weeks prior to Screening.
- Complete physical examination including full-body skin exam.
  - Physical examination includes: height, weight, general appearance, skin (other than primary diagnosis), HEENT (head, eyes, ears, nose and throat), heart (auscultation), lungs (auscultation), abdomen (palpation and auscultation), lower extremities (peripheral edema), neurologic (mental status, station, gait, reflexes, motor and sensory function, coordination) and lymph nodes.
- Vital signs [blood pressure (BP); heart or pulse rate; and oral, tympanic, or temporal temperature].
- Males are reminded that they must use effective measures to avoid pregnancy in their partner at all times, even after vasectomy, for 3 months after the last dose.
- Females are reminded that they must use 2 effective methods to avoid pregnancy for 1 month prior to start of study medication, during therapy, and for 9 months after completing therapy.
- For women who do not want to conceive in the future but are still women of childbearing potential:
  - Two negative pregnancy tests with a sensitivity of at least 25 mIU/mL at least 19 days apart
  - For patients with regular menstrual cycles, the second pregnancy test should be done during the first 5 days of the menstrual period immediately preceding the beginning of therapy and after the patient has used 2 effective measures to avoid pregnancy for 1 month.
  - For patients with amenorrhea, irregular cycles, or using a contraceptive method that precludes withdrawal bleeding, the second pregnancy test must be done immediately preceding the beginning of therapy and after the patient has used 2 effective measures to avoid pregnancy for 1 month.
- Laboratory evaluation at baseline to evaluate abnormalities in hematocrit/platelet counts, renal or hepatic function and electrolytes.

#### 6.1.1.1 **Target lesion selection**

- If multiple lesions are deemed to be suspicious for basal cell skin cancer on visual inspection, up to 4 lesions will be considered for investigation and designated "potential target lesions". Potential target lesion(s) will be selected at clinician discretion using clinical and dermoscopic findings and in consideration of patient preference.
- Measurement pre- and post-biopsy and high resolution digital photography of potential target lesion(s).

- Template map drawing of clinically evident tumor margins and local landmarks using a permanent marker on a clear plastic overlay.
- To confirm diagnosis of BCC and to designate histologic subtype, up to three representative 2-mm or three representative 3-mm punch biopsies will be performed on each potential target lesion.
  - Skin biopsies performed at Pre-study Screening visit will comprise no more than 10% of visible lesion surface area.
  - Skin biopsies must be performed at least 1 mm from peripheral margin of visible lesion.
- Biopsy of each potential target lesion will be performed in area that clinically appears to be thickest by inspection at palpation. If the potential target lesion appears to be homogenous, the biopsy will be performed at the center of the lesion.
- Post-biopsy pre-treatment lesion area will also be recorded and template drawn.

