## 2. STUDY OBJECTIVES

### 2.1 PRIMARY OBJECTIVES

- To compare the efficacy of vismodegib in various histologic subtypes of high risk and/or locally advanced basal cell skin cancer

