## 9.2 SUBJECT SUB-GROUP ASSIGNMENT

A total of 36 subjects with infiltrative/morpheaform, nodular, or superficial BCC will be enrolled in the study. For patients with multiple BCC lesions, one “target lesion” will be identified and used for subject sub-group assignment for the purposes of enrollment and followed for primary endpoint analysis. For scientific purposes, data from BCC tumors other than “target lesion” will also be collected. The lesion(s) biopsied at Screening Visit will be reviewed and each subject will be assigned to a subtype group as detailed below and in Figure 5.

**Step 1.** Infiltrative/morpheaform subtype lesion will be given priority in subject sub-group assignment.

**Step 2.** If a potential subject does not have a possible target lesion that is infiltrative/morpheaform subtype and has a superficial BCC, then the subject will be assigned to the superficial BCC subtype group.

**Step 3.** If no infiltrative/morpheaform BCC or superficial BCC are identified, then nodular BCC will be eligible for enrollment.

[figure not shown]

Figure 5. Target Lesion Assignment Algorithm

If there are two lesions that may be eligible for target lesion assignment based on histologic subtype, then the lesion with larger clinical dimensions will be designated the “target lesion”. See Appendix 10, Target Lesion Assignment Examples for more information.

This “Target Lesion Assignment Algorithm” will continue in this fashion until any two of the subtype groups reaches 26. This is to ensure that each subgroup has at least 10 subjects. At this point, subjects enrolled must have at least 1 BCC of the remaining subtype group.

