GF6	I am enjoying the things I usually do for fun .....	0	1	2	3	4
GF7	I am content with the quality of my life right now .....	0	1	2	3	4

If a patient has multiple BCC tumors, target lesion assignment will be based on histology using algorithm in Figure 2.

Histology is the primary consideration for “target lesion assignment.” Histology trumps size. Size is only considered if there are two lesions that may be eligible for target lesion assignment based on histologic subtype. In this case, the lesion with larger clinical dimensions will be designated the “target lesion”.

See Example 1 and Example 2 for more details.

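### Nothing requires the target lesion itself to meet inclusion criterion 4, so in subjects with several BCCs the primary-endpoint lesion can lie outside the high risk or locally advanced population

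*Combined protocol and SAP*

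**What the plan says.** The primary objective (Section 2.1) is "To compare the efficacy of vismodegib in various histologic subtypes of high risk and/or locally advanced basal cell skin cancer".

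Inclusion criterion 4 (Section 4.1) applies to the subject, who "Has one or more clinically suspicious lesions for BCC at Pre-Study screening Visit that is/has" at least 6 mm on mask areas, genitalia, hands or feet, at least 10 mm on cheeks, forehead, scalp or neck, or at least "20 mm if located on trunk and extremities". The alternative is a lesion suspicious for locally advanced BCC: 10 mm or more, recurrent or deforming to resect, and unsuitable for radiation. Criterion 5 asks for a confirmed BCC without tying it to the lesion that met criterion 4.

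Under Section 6.1.1.1, if several lesions look suspicious, "up to 4 lesions will be considered for investigation and designated" potential target lesions. The choice among them is described as follows: "Potential target lesion(s) will be selected at clinician discretion using clinical and dermoscopic findings and in consideration of patient preference".

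Section 9.2 assigns the target in order: infiltrative/morpheaform, then superficial, then nodular. If two lesions are eligible on subtype, "then the lesion with larger clinical dimensions will be designated the" target. Appendix 10 adds: "Histology trumps size. Size is only considered if there are two lesions that may be eligible for target lesion assignment based on histologic subtype". That single lesion determines the subject's subtype group and is followed for the primary endpoint.

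**The concern.** Eligibility is judged on one lesion and efficacy may be judged on another. The sections that define the target refer to suspicion, discretion, subtype and size, but not to the criterion 4 definition. The objective is limited to high risk or locally advanced BCC, so a target that meets neither definition does not belong in the comparison.

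The comparison between subtypes is also exposed. Subtype priority tends to move non-qualifying lesions into the superficial and infiltrative groups, because a nodular qualifying lesion gives way to any superficial or infiltrative one. Section 1.1 calls tumor size predictive of outcome, and Section 1.2 describes superficial BCC as non-aggressive and more often at low-risk sites. A difference between subtypes could then partly reflect size or risk class. Section 9.3.3.1.1 plans to examine gender, race and anatomic location, but not baseline size or criterion 4 status. In a group of 10, each non-qualifying target carries 10 percentage points of the response rate.

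**Working it through.** **The plan's own figures.** The plan gives none for this point. The nearest are the Section 9.1 confidence intervals, which are Wald intervals, p ± 1.96·√(p(1−p)/n):
- n = 16, p = 0.75: 0.75 ± 0.212, giving 53.8%-96.2% (stated 54%-96%).
- n = 10, p = 0.40 (implied by the interval, not stated): 0.40 ± 0.304, giving 9.6%-70.4% (stated 10%-70%).

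They reproduce, and they treat every target as evaluable for the objective. If only 8 of 10 targets qualified, the interval at 40% would be 6.1%-73.9%.

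**Tracing the rules.** A subject has a 12 mm nodular BCC on the nose and an 8 mm superficial BCC on the trunk.
1. The nasal lesion satisfies criterion 4 (12 ≥ 6 mm). The trunk lesion does not: 8 < 20 mm, and 8 < 10 mm rules out locally advanced.
2. Both look suspicious, so both may enter the pool.
3. There is no infiltrative lesion, so Step 2 makes the 8 mm trunk lesion the target.

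The tie-break does not repair this, because the limits depend on site. Of two superficial lesions, 15 mm on the trunk (below 20 mm, assumed not locally advanced) outranks 8 mm on the eyelid (above 6 mm).

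**Lower size bound.** Section 6.1.1.1 limits screening biopsies to 10% of the visible surface. One 2-mm punch removes π·1² = 3.14 mm². The lesion must then be at least 31.4 mm², which for a round lesion is a diameter of 2·√(31.4/π) ≈ 6.3 mm. This exceeds the 6 mm limit, so a round lesion on a mask area, genitalia, hand or foot qualifies if it can be biopsied within the cap. The gap is about 6.3-10 mm on cheek, forehead, scalp or neck, and 6.3-20 mm on trunk or extremities (from 10 mm up, only if not locally advanced). The 8 mm example passes the cap: 4/64 = 6.25%.

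**Possible frequency.** Assumptions not in the documents: exactly one of k biopsied BCCs qualifies, and subtype is independent of qualifying. With i, s and n the infiltrative, superficial and nodular shares, and ties always resolved in favor of the qualifying lesion:

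P(non-qualifying target) = n·[1 − n^(k−1)] + s·[1 − (1 − i)^(k−1)]

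Section 1.2 gives nodular 70% and 10-15% for each of the others. I used 70/15/15, and 80/10/10 as a lower-end assumption. For k = 2 these give 0.70·0.30 + 0.15·0.15 = 0.2325 and 0.80·0.20 + 0.10·0.10 = 0.17.

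| k | 80/10/10 | 70/15/15 | Ties unrelated to risk (1 − 1/k) |
|---|---|---|---|
| 2 | 17% | 23% | 50% |
| 3 | 31% | 40% | 67% |
| 4 | 42% | 52% | 75% |

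In the first two columns every non-qualifying target falls in the infiltrative or superficial group.

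**Trial level.** If 10% to 50% of the 36 subjects had several BCCs (assumption), the expected count runs from 36 × 0.10 × 0.17 = 0.6 to 36 × 0.50 × 0.518 = 9.3 before tie-break errors, and to 36 × 0.50 × 0.75 = 13.5 with ties unrelated to risk.

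**The case against.** The strongest reply is that a linked reading was intended. Criterion 4 and Section 6.1.1.1 both speak of suspicious lesions, Section 6.1.1 reads the histologic criterion as being about the target, and Section 6.3.2 excludes a subject whose target is not BCC. A site could well assume that potential targets must meet criterion 4. But this is not written, and two sites may read it differently. Figure 5 is not shown and the Section 9.2.1 cited in Section 6.1.2 is not visible, so the finding rests on the text of Section 9.2 and Appendix 10.

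Other replies stand in part. Size and site are recorded for each lesion, so criterion 4 size and site status can be derived later; but a lesion that was not made the target cannot be restored as the target by analysis. The study is a pilot with wide intervals. The sample size was chosen to secure non-nodular subtypes, so restricting the pool has a real recruitment cost.

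A reader might infer more than the documents support:
- That the objective is in fact tested on the wrong lesions. It can be; a subject whose only BCC met criterion 4 is unaffected.
- That the target is chosen on histology alone. Clinical pre-selection comes first and size breaks ties, but neither step tests criterion 4.
- That the shift only ever spares the nodular group. Ties can yield non-qualifying nodular targets. So can the late fill rule in Section 9.2: once two groups reach 26, new subjects need a BCC of the remaining subtype.
- That every small infiltrative target is outside the population. Section 1.1 leaves high-risk features to a guideline that Appendix 1 only links, and Section 1.2 calls this subtype aggressive. The documents do not settle it.
- That smaller lesions clear more easily. No passage says so, and partial response and progression are relative to diameter. Confounding is possible; its direction is not established.

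**Conclusion.** The concern holds in limited form. As written, the rules can make a lesion that does not meet criterion 4 the primary-endpoint lesion in a subject with several BCCs. The clear case is a superficial lesion of about 6.3-20 mm on trunk or extremities, or 6.3-10 mm on cheek, forehead, scalp or neck, that is not locally advanced.

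The size of the problem is unknown. The 17-23%, 31-40% and 42-52% figures for 2, 3 and 4 lesions apply only to multi-lesion subjects, and rest on exactly one lesion qualifying and on independent subtypes. If a second lesion qualified half the time, the two-lesion figure would halve, to about 9-12%. This should be fixed because it concerns which lesion answers the primary question, but it does not by itself invalidate the design.

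**What to change.** State in Sections 6.1.1.1 and 9.2 and in Appendix 10 that a lesion can be a potential target only if it individually meets the size/site limits or the locally advanced definition of criterion 4. Apply Steps 1-3 and the larger-dimension tie-break among those lesions only. Keep all other BCCs as non-target lesions; Section 9.2 already provides for collecting their data.

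For any subjects already enrolled, derive each target's criterion 4 status from the recorded size and site (with the locally advanced elements where these were documented), and report the primary comparison restricted to qualifying targets beside the full one.

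The cost is a sentence in each of three places and no added procedure. The downside is that the superficial and infiltrative groups may fill more slowly, chiefly because of the 20 mm limit on trunk and extremities. The documents do not allow that delay to be quantified.

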### **6.1.2 Treatment Initiation Visit (Baseline/Day 1)**

The objective of this visit is to ensure that subjects who will enter the study continue to meet all inclusion and exclusion criteria and to perform baseline evaluations of the biopsy-confirmed BCC target lesion site.

For subjects with >1 histologically-confirmed BCC identified at Pre-study Screening Visit, target lesion assignment for primary endpoint analysis is described in Section 9.2.1 Target lesion assignment.

The study visit should occur within 4 weeks of Pre-study Screening visit.

The following procedures will be performed at Treatment Initiation Visit (Baseline/Day 1) after confirmation that the subject has met all inclusion criteria and has no exclusion criteria present:

- Assessment of any changes (deletions, additions, or dose modifications) to medications.
- Complete physical examination including general appearance, skin exam, and visual inspection of target lesion.
- Vital signs (BP; heart or pulse rate; and oral, tympanic, or temporal temperature).
- Weight and height measurements.
- Urine pregnancy test ( $\alpha$ -hCG) for women who are of childbearing potential.
- Photography and measurement of target lesion(s) with ruler visible in photographic field
- Template map drawing of clinically evident tumor margins and local landmarks using a permanent marker on a clear plastic overlay.
- Complete an evaluation of target tumor, including:
  - Tumor measurement/dimensions Photograph target lesion
  - Adverse Event (AE) Monitoring.
- Subjects will complete the Patient Reported Outcomes (PRO) questionnaire: SKINDEX-16 to obtain baseline information. (Appendix 6)
- Dispense study drug bottles.
- Provide appropriate training and specific written instructions for study drug (capsules) self-administer by subject.

- Observe subject administer first dose of study drug (on Day 1 only)
- Review subject diary and instructions on completion for daily dosing/drug accountability. The subject will be instructed to begin data diary recording at home.
- Reminder to use effective measures to avoid pregnancy
- Subject will be given written instructions for adverse event monitoring, measures to avoid pregnancy and avoiding of blood production products (Appendix 7.)

